8.2 Endpoints

Primary Efficacy Endpoint

The primary endpoint is complete remission at 24 weeks. Complete remission is defined as an IgG4-RD Responder Index Score of 0 and a prednisone dose of 0 mg/day and no flare since beginning treatment.

Secondary Efficacy Endpoints

- Disease response at 4, 12, 24, and 36 weeks. Disease response will be defined at 6 months as: 1) improvement of ≥ 1 point in the IgG4-RD RI score over baseline; 2) no glucocorticoid use following the week 4 visit; 3) no disease flares, as assessed by the IgG4-RD RI. Disease flare will be defined as recurrence of disease activity or demonstration of a disease exacerbation such that additional therapy beyond the trial protocol is indicated. Such additional therapy may include glucocorticoids or alternative immunosuppressive agents.
- Complete remission at 36 weeks.
- Time to disease remission (IgG4-RD RI = 0)
- Remission rates

- Number of disease flares per subject over time
- Cumulative corticosteroid doses and Glucocorticoid Toxicity Index
- Physician Global Assessment (PGA). A PGA consisting of a 10-centimeter visual analog scale is collected at each patient visit. Only active disease (as opposed to damage) is considered in the scoring of the PGA.
- Symptom Severity Index
- Serum immunoglobulin levels, IgG4 subclass concentrations, IgE levels, eosinophils, and serum C3 and C4

Safety Endpoints

Safety analyses will be performed using all treated subjects.

- The number and percent of subjects experiencing a treatment-emergent adverse event will be tabulated for each coded MedDRA system-organ class and preferred term. Treatment-emergent adverse events will also be tabulated according to intensity and causality.
- All SAEs, discontinuations due to AE, or deaths occurring during the course of the trial will be presented in subject listings.
- The number and percent of subjects experiencing a glucocorticoid-related AE will be tabulated for each coded MedDRA system-organ class and preferred term. Treatment-emergent adverse events will also be tabulated according to intensity and causality.
- Clinical laboratory tests (observed values) will be summarized descriptively in tabular format. Shift tables will be presented for select laboratory parameters. In the subject listings, values outside of the laboratory's reference limits will be identified, along with the Investigator's assessment of clinical significance. A list of all normal laboratory ranges will also be provided. Clinically significant laboratory test abnormalities that were considered AEs by the Investigator will be presented in the AE listings.
- Vital signs (BP, pulse, temperature) will be summarized (observed and change from baseline) at each visit vital signs are collected using descriptive statistics and subject listings.
- Concomitant Medications will be summarized by the number and percentage of subjects in each therapeutic class and preferred term as coded using the WHODrug dictionary.

Physical Examinations will be presented in subject listings.

8.3 Quality of Life Assessments

Quality of life assessments will include the Physician Global Disease Activity Assessment Visual Analogue Scale (PhGA VAS), the Patient Global Disease Activity Assessment VAS (PtGA VAS), the Symptom Severity Index and the 36-item short form health survey (SF-36). Unless otherwise specified, the QOL analyses will include all randomized subjects who have a non-missing baseline and at least one post-baseline QOL assessment. Subjects in this subset

will be analyzed according to their randomized treatment assignment, regardless of treatment received.

The percentage of participants randomized to each treatment group who complete the QOL questionnaires at each assessment point after baseline (i.e., QOL completion rates) will be calculated and compared. If significant differences in QOL completion rates are observed, additional analyses may be performed to evaluate the potential for reporting biases.

For each QOL endpoint, descriptive statistics will be presented for recorded values at each visit, including mean, standard deviation, median, minimum, maximum, change from baseline and percent change from baseline.

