5 INVESTIGATIONAL PLAN

Overall Study Design and Plan

Description

This is a Phase 2, prospective, open-label, single center clinical trial in subjects with active IgG4-RD. Approximately 10 subjects with active IgG4-RD will be enrolled. After screening and enrollment, eligible subjects will receive an initial subcutaneous dose of abatacept (125mg) followed by weekly subcutaneous doses of abatacept (125mg) for a total of up to 24 doses (24 weeks). Subjects will be followed on study for 12 weeks following the last dose for a total study period of up to 36 weeks.

After obtaining informed consent, all screening procedures and tests establishing eligibility will be performed on the initial screening visit. Subjects determined to be eligible at screening will receive an initial subcutaneous dose of abatacept (125mg), which will be continued weekly for a total of up to 24 doses (24 weeks). Steroid therapy must be tapered off and discontinued over a 4 week period (taper must be completed no later than week 4). Should patients be deemed to have worsening disease or failing therapy at 4 weeks then a trial of steroids can be considered.

Subjects will return on weeks 1, 2, 4, 8, 12, 16, 20, and 24 while on treatment for their injections, and for the scheduled safety and disease response assessments. Subjects will be allowed to self-administer their injections at home. The full treatment period is 24 doses given weekly for 24 weeks. Subjects who are not able to be tapered off corticosteroids or who require reinstitution of corticosteroid therapy at any time during the study will be counted as treatment failures but may continue on study. Should the IgG4-RD responder index fail to improve by 8 weeks or who develop new organ involvement by week 4 will be deemed a treatment failure, patient's will be deemed treatment failure and can begin corticosteroid or alternative immunosuppressive therapy at the Investigator's discretion. Those who require rituximab or who require addition of other oral immunosuppressive will be counted as treatment failures and will terminate the study.

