5.3 Discussion of Study Design

No therapies for IgG4-RD have been approved by regulatory authorities and thus there are no established study designs for this disease indication. This study design is consistent with the focus of this trial on proof-of-concept and mechanistic studies and will be suitable to achieve this goal based on the strict primary outcome criteria. There is no control group in this proof of concept study. The design will be able to assess whether abatacept can have an effect on disease response as has been shown in a prior case report as discussed above. The design of this trial is appropriate to our current understanding of the potential role of abatacept in IgG4-RD, which is presently too limited to justify a randomized trial. Should patients fail to respond to the study drug abatacept or should they develop end-organ manifestations, they will be able to obtain standard of care glucocorticoid treatment.

A washout period is built into the study protocol. Exclusion criteria include the prior use of rituximab (or other B cell depleting agents) within 6 months of enrollment unless B cells have been demonstrated to have repopulated or the use of any investigational agent within 5 half-lives of the agent (or 6 months if the half-life is unknown) prior to enrollment. This should be sufficient in identifying any adverse effects due to the investigational product abatacept. However, patient's may have been on glucocorticoids during trial entry, but must be willing to taper off of glucocorticoids within ~~4~~ 8 weeks of beginning abatacept. This is necessary in order to sufficiently recruit patients for the study.

The investigational medication abatacept is dosed weekly by subcutaneous route which is consistent with its pharmacokinetic and pharmacodynamic profile. It is approved for the treatment of rheumatoid arthritis at this dosing interval. These medications may be continued indefinitely for control of the disease and any effect should be seen within 24 weeks of treatment.

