5.6 Withdrawal of Subjects

Subjects are encouraged to complete all study evaluations. However, they may withdraw from the study at any time and for any reason. Every effort will be made to determine why any subject withdraws from the study prematurely. All subjects who withdraw from the study with an ongoing AE must be followed until the event is resolved or deemed stable. At the time that a subject withdraws prematurely for any reason, all assessments as listed for the EOS visit should be performed. If a subject withdraws prematurely after dosing, all data to be collected prior to discharge from the clinical site will be collected at the time of premature discontinuation or at the scheduled end-of-study visit. Subject participation may be terminated prior to completing the study and the reason recorded as follows:

1. Adverse event
2. Protocol violation

3. Loss to Follow-up
4. Subject withdrew consent
5. Investigator withdrew subject to give rescue therapy other than steroids
6. Other

A comprehensive effort must be made to determine the reason(s) why a subject fails to return for the necessary visits or is discontinued from the study. If the subject is unreachable by telephone, a registered letter, at minimum, should be sent to the subject requesting him/her to contact the study site.

Subjects withdrawn due to AEs considered to have a possible relationship to study drug will not be replaced. Subjects withdrawn for a non-drug related reason will be replaced if deemed necessary by the Sponsor. The decision regarding the replacement of subjects will be documented.

If a subject withdraws prematurely, all assessments as listed for the EOS visit should be performed and recorded on an unscheduled visit eCRF page. In addition, the subject should be scheduled for a follow-up visit 4 weeks from the time of the last injection of study drug, at which time all assessments as listed for the EOS visit should be performed.

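### By-visit means of PGA, Symptom Severity Index and SF-36 lose subjects who must leave for non-steroid rescue, and the only check on missing scores cannot work in one arm

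*Protocol*

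**What the plan says.** Section 8.3 covers the physician and patient global scales, the Symptom Severity Index and the SF-36. For each of them "descriptive statistics will be presented for recorded values at each visit", including change and percent change from baseline. The analysis set is subjects "who have a non-missing baseline and at least one post-baseline QOL assessment". Section 8.3 also has completion rates calculated after baseline and compared between randomised groups, with further analyses optional if the rates differ significantly.

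The study description in Section 5 (repeated in the synopsis) sets the exit rule: "Those who require rituximab or who require addition of other oral immunosuppressive will be counted as treatment failures and will terminate the study". Section 5.6 lists as a reason for ending participation "Investigator withdrew subject to give rescue therapy other than steroids". For a premature withdrawal, Section 5.6 says that "all assessments as listed for the EOS visit should be performed and recorded on an unscheduled visit eCRF page", and it adds a visit four weeks after the last injection with the same assessments. Another sentence in Section 5.6 allows withdrawal data to be collected either at discontinuation or at the scheduled end-of-study visit.

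On design, "Approximately 10 subjects with active IgG4-RD will be enrolled" (Section 5) and "There is no control group in this proof of concept study" (Section 5.3). PGA and the Symptom Severity Index are secondary efficacy endpoints (Section 8.2), and the effect of abatacept on them is a secondary objective (Section 4.2).

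**The concern.** The exit rule creates missing values that depend on outcome. A subject leaves because the disease was not controlled, so those who remain at later visits are, on average, likely to be the better responders. A mean over recorded values can then improve from visit to visit with no individual improving further.

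With no control group and about 10 subjects, the course of these means over time is the trial's evidence on PGA and symptoms. The binary endpoints do not have this weakness, because subjects who exit for rescue count as failures and Section 8.4 takes percentages over the total in the analysis population. Being counted as a failure has no effect on a mean.

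**Working it through.** The protocol states no expected score, standard deviation or withdrawal rate for these scales, so there is no figure to reproduce. The check has two parts.

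**1. Following one subject through the text.** Suppose a subject needs another oral immunosuppressive at week 12.

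- Section 5: the subject is a failure and leaves the study. Such exits can come well before week 24, since Section 5 allows failure to be declared on week-4 or week-8 findings and alternative immunosuppression to follow.
- Section 5.6: the exit assessments go on an unscheduled page. The end-of-study column of the schedule in Section 5.1 includes the physician scale, the Symptom Severity Index and the SF-36, so the scores exist.
- Section 5.6: the extra visit is tied to the last injection. If that was at week 12, the visit falls at 12 + 4 = week 16. It would fall near week 24 only if the last injection was near week 20 (20 + 4 = 24). It cannot reach week 36 under the planned dosing, which ends by week 24 (24 + 4 = 28).
- Section 8.3: the subject has post-baseline values and so belongs to the analysis set, but has no recorded value at week 24 or week 36.

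A subject who exits between weeks 24 and 36 has a week-24 value and is missing only at week 36.

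**2. Size, as an illustration.** Let N = 10 (Section 5), let k be the number who left before the visit, let m be the mean score of those who stay, and let d be how much worse the leavers score, in mm on the 100 mm scale. Both k and d are assumptions.

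- Recorded-value mean = m
- Mean over all N = [(N − k) × m + k × (m + d)] / N = m + (k/N) × d
- Difference = (k/N) × d

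| Leavers k | Subjects in the mean | d = 20 mm | d = 40 mm | d = 60 mm |
|---|---|---|---|---|
| 1 | 9 | 2 mm | 4 mm | 6 mm |
| 2 | 8 | 4 mm | 8 mm | 12 mm |
| 3 | 7 | 6 mm | 12 mm | 18 mm |

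The chance of at least one leaver among 10, taking an independent risk q per subject, is 1 − (1 − q)^10. For assumed q of 5%, 10%, 20% and 30% this gives 40%, 65%, 89% and 97%.

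**The safeguard.** Completion rates can be calculated in one arm, but the comparison that would prompt further analysis needs two groups. It can never be triggered here.

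**The case against.** The strongest objection is that Section 8.3 does not say recorded values are the only summary, and that an unscheduled page is a data-capture instruction. No sentence excludes those values from analysis, and mapping early-termination visits is ordinary content for a statistical analysis plan, which is not at hand. This stands in part: the point cannot rest on the lack of an imputation rule. It rests on what the protocol itself fixes, namely outcome-driven exit, off-visit filing, by-visit summaries of recorded values, and a bias check written for a randomised trial.

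Several stronger readings are tempting, and the documents do not support them.

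- A reader might infer that all poor outcomes disappear from the means. Subjects who need steroids count as failures but may stay, so their scores remain, although they then reflect the rescue.
- A reader might infer that attrition is hidden. Section 8.4 reports n with each continuous summary and Section 8.3 calculates completion rates, so a fall from 10 to 8 would show. Neither shows that those missing left for rescue, or what they scored.
- A reader might infer that no week-36 value can exist for a leaver. The sentence in Section 5.6 that allows collection at the scheduled end-of-study visit leaves that open, and it does not fit with the unscheduled-page sentence.
- A reader might express the effect as a percentage overstatement. If leavers did not change at all, it would be 10/(10 − k) − 1, or 11%, 25% and 43% for k = 1, 2 and 3. Nothing in the documents supports zero change, and partial improvement before exit would reduce these figures.

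These are also descriptive secondary summaries on which no test or decision rule in the protocol depends. That limits the weight of the point but does not remove it.

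**Conclusion.** The concern holds for the PGA, Symptom Severity Index and SF-36 summaries at weeks 24 and 36, and only for subjects who leave the study. Non-steroid rescue is the exit route that selects on poor outcome. If leavers score worse than those who stay, the later means are too favourable by (k/10) × d. Over the assumed ranges above that is 2 to 18 mm. The direction follows from the text, while the size rests wholly on assumed k and d.

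Complete remission and disease response are not affected in this way. The matter is worth correcting because the exit scores are already to be collected and the one safeguard provided cannot function. It does not threaten the primary result.

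**What to change.** Keep the by-visit summaries in Section 8.3 and make four additions or changes.

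1. Add a supportive summary at week 24 and at week 36 over all treated subjects with a baseline value. Use the scheduled value for those still on study and the withdrawal assessment for those who left earlier. Name the withdrawal assessment specifically, because the visit four weeks after the last injection may already reflect rescue.
2. Beside each mean, show n, the number who had left and the number who exited for rescue. Flag these subjects in the listing.
3. Replace the between-group comparison of completion rates with completion rates by visit and reasons for missing values.
4. Reconcile the two sentences in Section 5.6 on when withdrawal data are collected and where they are recorded.

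Report the supportive summary next to the by-visit means and not as the sole basis for the stated effect. It mixes time points, since exit values come from earlier weeks, and it has the usual limits of carrying a last value forward. The cost is one additional table and some text. It needs no new visits or data, and no change to the exit or rescue rules.

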8.4 Statistical Methods General

Considerations

Summary statistics will be presented by way of n, mean, standard deviation (SD), median, minimum and maximum for continuous variables and by way of group frequencies and percentages for categorical variables. Percentages will be calculated using the total subjects per arm in the planned analysis population, unless specified otherwise.

For listings, in the cases where a subject's record has been continued to the next page, an appropriate identification (e.g., the subject ID number) must be presented at the beginning of that page.

Unless otherwise specified, in summary tables of continuous variables, the minimum and maximum values will be displayed to the same number of decimal places as the raw data, the mean and median will be presented to one extra decimal place compared to the raw data, and the standard deviation will be displayed to two extra decimal places compared to the raw data. Wherever possible, data will be decimal aligned.

Unless otherwise specified frequency tabulations will be presented by number and percentage, where the percentage is presented in brackets to 1 decimal place.

P-values, if applicable, will be presented to 3 decimal places. If a p-value is less than 0.05 but is greater than or equal to 0.01, then an asterisk (*) will be added next to this value. If a p-value is less than 0.01 but is greater than or equal to 0.001, then two asterisks (**) will be added next to this value. Finally, if the p-value is less than 0.001 then three asterisks (***) will be added next to this value and it will be presented as <0.001. If the rounded result is a value of 1.000, it will be displayed as >0.999.

9 DIRECT ACCESS TO SOURCE DATA/NOTES

The Investigator will ensure the accuracy, completeness, and timeliness of the data reported to the Sponsor. Data collection processes and procedures will be reviewed and validated to ensure completeness, accuracy, reliability, and consistency.

The Investigator or designee will prepare and maintain adequate and accurate study documents (medical records, ECGs, AE and concomitant medication reporting, raw data collection forms, etc.) designed to record all observations and other pertinent data for each subject receiving IMP.

The Investigator will allow Sponsor representatives, contract designees, authorized regulatory authority inspectors, and the Institutional Review Board (IRB)/ Independent Ethics Committee (IEC) to have direct access to all documents pertaining to the study.

10 QUALITY CONTROL AND QUALITY ASSURANCE

Data Quality Assurance

The Investigator must prepare and maintain adequate and accurate records of all observations and other data pertinent to the clinical study for each study participant. Frequent communication between the clinical site and the Sponsor is essential to ensure that the safety of the study is monitored adequately. The Investigator will make all appropriate safety assessments on an ongoing basis. The Sponsor's medical representative may review safety information as it becomes available throughout the study.

All aspects of the study will be carefully monitored with respect to GCP and SOPs for compliance with applicable government regulations.

The study may be audited to assess adherence to the Clinical Study Protocol. The Investigator/investigational site will permit study-related monitoring, audits, IRB/IEC review and regulatory inspections by providing direct access to source data/documents. Direct access includes permission to examine, analyze, verify, and reproduce any records and reports that are important to the evaluation of a clinical study.

During the conduct of the study, process-related audits may be performed as well. An audit certificate will be provided in the final study report outlining the audit performed and other related activities.

11 ETHICS

11.1 Independent Ethics Committee/Institutional Review Board

Prior to the start of the study, the investigator is responsible for ensuring that the protocol and consent form have been reviewed and approved by a relevant IEC/IRB. The IEC/IRB shall be appropriately constituted and perform its functions in accordance with FDA ICH GCP and local requirements as applicable.

The IEC/IRB shall approve all protocol amendments (except for logistical or administrative changes), written informed consent documents and document updates, subject recruitment procedures (e.g., advertisements), written information to be provided to the subjects, investigator's Brochure, available safety information, information about payment and compensation available to subjects, the investigator's curriculum vitae and/or other evidence of qualifications and any other documents requested by the IEC/IRB and Regulatory Authority (Competent Authority) as applicable.

11.2 Good Clinical Practice

The procedures set out in this clinical study protocol are designed to ensure that the Sponsor and the Investigator abide by the principles of the ICH guidelines on GCP as outlined in CPMP/ICH/135/95 and the Declaration of Helsinki (Version 2008). The clinical study also will be carried out in keeping with national and local legal requirements (in accordance with United States Investigational New Drug [IND] regulations [21 CFR Parts 50, 56 and 312]).

The Investigator will be responsible for the care of the subjects throughout the study. If the Investigator is not present at the study site, he/she will leave instructions for the staff and a telephone number where he/she can be reached.

